3.2 Secondary objectives

The secondary objective of the study is to describe and compare between patients with and without persisting COVID-19 the clinical, virological and radiological outcomes and the different therapeutic approaches performed.

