3.3 Endpoints

The first primary endpoint variable will be the prevalence of persisting SARS-CoV-2 infection among the immunocompromised patients defined as the persistence or the recurrence of symptoms and signs (fever, dyspnea, hypoxemia, changes on chest-X ray or CT scan) and positive SARS-CoV-2 PCR ≥ 21 days after the time 0 (day of the first test positive for SARS-CoV2 infection).

The endpoints for the secondary objectives are:

- Duration of treatment carried out to address the persistent COVID-19 condition and treatment-related adverse effects.
- Duration of viral shedding, defined as the number of days between the first positive test and first negative PCR test.
- Duration of symptoms, defined as the number of days between symptoms onset and the clinical cure.
- Prevalence of imaging alterations, defined as the presence of new ground-glass and/or crazy paving and/or interstitial infiltrates at chest CT scan during the persisting infection (starting from 21 days after the first positive test until viral clearance).
- Re-infection within 120 days, define as new positive test with or without symptoms after viral clearance has been achieved.
- All-cause 120-day mortality.

4. Investigational plan

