4.3 Study design

Spontaneous international multicenter retrospective and prospective observational study.

The retrospective recruitment period will span from 1.01.2022 to the date of authorisation by hospital directorates following the Ethics Committees' approvals. This period has been established considering the prevalent diffusion of the omicron variant and its subvariants, which has led to significant changes in the clinical manifestations of COVID-19. The prospective recruitment will be carried out over the 12 months immediately following the retrospective period.

During the study period, screening for persisting SARS-CoV-2 infection and therapeutic management of all patients will be carried out by the attending physicians according to routine practice.

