4.4.3 Population size of the study and statistical power

According to the records of the Haematology Unit of IRCCS AOU of Bologna, from January 2022 to December 2022, 250 patients with underlying B cell malignancies have been diagnosed with SARS-CoV2 infection and we estimate that approximately 30% had viral shedding longer than 21 days. Thus, we deem that at the end of the study period, approximately 500 patients will be enrolled from IRCCS AOU of Bologna of which about 150 with prolonged infection. Considering the epidemiology of the other participating centers, we expect to reach an overall cohort of about 1000 immunocompromised patients with SARS-CoV-2 infection, with approximately 300 prolonged infections.

Power analysis carried out using Stata v.17.0 showed that a sample size of 1,000 allows to obtain power=80% and alpha=0.05 for a log-rank test comparing 120-days mortality, with a 300/700 allocation ratio, when the difference in mortality rates is at least 4% and mortality rate in the non-persistent COVID is as low as 3%, or when the difference in mortality rates is at least 5% and mortality rate in the non-persistent COVID is at least 4%.

Estimated sample sizes for two-sample comparison of survivor functions
 Log-rank test, Freedman method
 H0: HR = 1 versus Ha: HR != 1

alpha	power	N	N1	N2	nratio	E	delta	hratio	s1	s2	Pr_E
.05	.8	897	627	270	.43	59	2.054	2.054	.95	.9	.06503
.05	.8	1,343	939	404	.43	84	1.839	1.839	.95	.91	.06203
.05	.8	2,282	1,596	686	.43	135	1.626	1.626	.95	.92	.05902
.05	.8	4,900	3,426	1,474	.43	275	1.415	1.415	.95	.93	.05601
.05	.8	18662	13050	5,612	.43	990	1.206	1.206	.95	.94	.05301
.05	.843	.	1	1	.95	.95	.
.05	.8	561	392	169	.43	33	2.581	2.581	.96	.9	.05804
.05	.8	768	537	231	.43	43	2.31	2.31	.96	.91	.05503
.05	.8	1,140	797	343	.43	60	2.043	2.043	.96	.92	.05203

	.05	.8	1,918	1,341	577	.43	94	1.778	1.778	.96	.93	.04902	
	.05	.8	4,070	2,846	1,224	.43	188	1.516	1.516	.96	.94	.04601	
	.05	.8	15304	10702	4,602	.43	659	1.257	1.257	.96	.95	.04301	
	.05	.8	367	256	111	.43	19	3.459	3.459	.97	.9	.05105	
	.05	.8	471	329	142	.43	23	3.096	3.096	.97	.91	.04804	
	.05	.8	638	446	192	.43	29	2.737	2.737	.97	.92	.04503	
	.05	.8	933	652	281	.43	40	2.383	2.383	.97	.93	.04203	
	.05	.8	1,545	1,080	465	.43	61	2.031	2.031	.97	.94	.03902	
	.05	.8	3,221	2,252	969	.43	116	1.684	1.684	.97	.95	.03601	

s1, s2 = survival rates in groups 1 and 2
 N1, N2 = sample size required in groups 1 and 2.

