4.7 Data management

Pseudonymized data will be collected using a pre-established electronic case report form (eCRF) developed using the REDCap capture tool hosted by CINECA, the Italian partner in charge of data management within the EU H2020 ORCHESTRA project. All centers will enter their data locally on the eCRF through internet connection. The principal investigator and/or her/his delegate will have access to all data in order to check for data integrity and advancement of data collection. Data sources will be clinical charts and hospital electronic records.

During all the study period, the principal investigator will inform investigators about the status of patient enrolment, follow-up, and data collection by newsletter periodically.

At the end of data collection, the principal investigator will be responsible for reviewing all data for integrity and accuracy. Queries will be generated and when necessary sent to

the local investigators for reviewing incomplete or inaccurate data. The database will be locked after fulfilment of all the queries.

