4.8 Statistical Analysis Plan

Patients' characteristics will be summarized using absolute frequencies and percentages (categorical variables) and mean±standard deviation or median and interquartile range (scale variables, according to their distribution).

The prevalence of persisting SARS-CoV-2 infection among the immunocompromised patients will be obtained as the ratio of the number of patients with evidence of persisting SARS-CoV-2 infection on the total number of enrolled patients.

As for the analysis of risk factors for persisting COVID, comparisons between COVID-persistent and non-persistent patients will be carried out by means of survival analyses for all outcomes expressed as durations (time-to-event analyses). These outcomes will be compared by estimating Kaplan-Meier curves, calculating log-rank tests and multiple Cox regressions in which COVID persistence will be the main risk factor and including the confounders and effect modifiers listed below.

- Age
- Sex
- Comorbidities (Charlson Comorbidity Index)
- Underlying hematologic disease state
- Chemotherapy treatments performed
- Duration of Hospital stay
- Admissions to intensive care
- Days with central venous catheter
- Bacterial and fungal superinfections
- Vaccination status
- Previous SARS-CoV-2 infections
- Serological status (anti-SARS-CoV-2 antibodies)

Re-infection and imaging alterations rates will be calculated as the ratio of the number of events to the overall number of patients, and the comparison between persisters and non-persisters will be carried out by calculating the corresponding risk ratios. A multiple logistic regression model will assess the relationship between exposure and re-infection (image alteration) net of the potential confounders.

For secondary aims, the secondary endpoints will be described just for the patients with persisting COVID, categorical variables will be reported as number and relative

frequencies, continuous variables will be reported as mean±SD or median and IQR according with their distribution.

5. Administrative procedures and declarations

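### Viral shedding ends at the first negative PCR under unscheduled testing, so clearance is interval-censored but analysed as an exact date, with an error whose net direction is unknown

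*Combined protocol and SAP*

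**What the plan says.** Section 3.3 gives the endpoint as "Duration of viral shedding, defined as the number of days between the first positive test and first negative PCR test". It does not ask for a confirming negative and does not use the date of the last positive.

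Section 4.3 says that "screening for persisting SARS-CoV-2 infection and therapeutic management of all patients will be carried out by the attending physicians according to routine practice". Section 4.7 adds: "Data sources will be clinical charts and hospital electronic records". No section sets a retest schedule, so the test dates are whatever care happened to produce.

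Section 4.8 says of outcomes expressed as durations: "These outcomes will be compared by estimating Kaplan-Meier curves, calculating log-rank tests and multiple Cox regressions". It names no interval-censored method. It has no rule for patients never shown negative or for those who die before a negative test.

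Two further points matter. First, persistence in Section 3.3 combines symptoms or signs that continue or come back with a "positive SARS-CoV-2 PCR ≥ 21 days after the time 0 (day of the first test positive for SARS-CoV2 infection"; positivity in between need not be continuous. Second, the plan disagrees with itself on how shedding is used. Section 3.2 sets out to "describe and compare between patients with and without persisting COVID-19 the clinical, virological and radiological outcomes", while the last paragraph of Section 4.8 says "the secondary endpoints will be described just for the patients with persisting COVID".

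**The concern.** The recorded duration mixes two things: how long the patient shed virus, and how long it was until someone tested again. Kaplan-Meier, log-rank and Cox methods in their usual form treat the event date as known. Here it is known only to fall within a window, and the width of that window is set by clinical habit.

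The rule also stops the clock at the first negative even when a later PCR is positive. This matters in a population chosen for prolonged and relapsing infection, and in a protocol whose own definition of persistence admits recurrence.

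At stake are the reported shedding times, which would be hard to interpret beside the 21-day threshold on which the study is built. Any contrast of shedding by centre, setting or covariate could also partly reflect how often patients were retested.

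**Working it through.** **Inputs from the documents.** Start: first positive test. End: first negative PCR (3.3). Persistence threshold: 21 days (3.3). Retest interval: not given. The only figure on shedding is in 4.4.3: "we estimate that approximately 30% had viral shedding longer than 21 days". The plan states no shedding duration to reproduce, and its sample size table concerns 120-day mortality only.

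**Inputs assumed.** Retest interval w of 3 to 28 days with a random starting point; true clearance time following a Weibull (shape 1.5, median 14 or 30 days) or a gamma (shape 2, mean 14 or 45 days); chance f of a false or transient negative at each test while still shedding of 0, 5% or 10%.

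**Step 1: the window, by example.** A patient is positive on day 7 and next tested, negative, on day 35. Clearance lies somewhere in the 35 − 7 = 28 days between, and the plan records 35. If this patient and another both cleared on day 10, and the other was tested on days 7 and 14, the plan records 35 for one and 14 for the other.

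**Step 2: accurate test (f = 0).** With a random starting point, the wait from clearance to the next test is uniform on 0 to w, so the mean excess is w/2 whatever the distribution of clearance:

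| Retest interval w (days) | 3 | 7 | 14 | 21 | 28 |
|---|---|---|---|---|---|
| Mean excess w/2 (days) | 1.5 | 3.5 | 7.0 | 10.5 | 14.0 |

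Simulation gives the same values. If two groups are retested at different intervals, the artefact is half the gap: (14 − 7)/2 = 3.5 days, or (28 − 7)/2 = 10.5 days. At equal intervals it cancels in the difference of means.

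**Step 3: one unconfirmed negative ends the clock (f > 0).** Mean error in days, recorded minus true:

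| True clearance | Tests every | f = 0 | f = 5% | f = 10% |
|---|---|---|---|---|
| Weibull, median 14 | 3 days | +1.5 | −1.6 | −4.0 |
| Weibull, median 14 | 7 days | +3.5 | +1.8 | +0.3 |
| Weibull, median 30 | 7 days | +3.5 | −2.8 | −7.7 |
| Gamma, mean 14 | 7 days | +3.5 | +2.1 | +0.9 |
| Gamma, mean 45 | 7 days | +3.5 | −6.6 | −13.8 |

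The sign changes. Long shedding and frequent testing give more chances of an early stop, so the error turns negative soonest in the patients this study is about.

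**Step 4: a contradiction that needs no assumptions.** A patient is positive on day 0, negative on day 12, and positive with recurrent symptoms on day 25. Since 25 ≥ 21, the patient is persistent under 3.3. Shedding under the same section is 12 days. Viral clearance has no separate definition, so the day-25 result could also be read as a new positive after clearance, that is, as a re-infection.

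**The case against.** The strongest reply is that this is one secondary endpoint in an observational chart study. The sample size rests on mortality, and the primary endpoint does not use the first-negative date. All of that is true. It limits the importance of the point but does not make the recorded dates exact.

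Several stronger readings are tempting, and the documents do not support them.

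- *Shedding is biased long.* A reader might infer this from Step 2 alone. Step 3 shows that the early stop can outweigh the test delay. Neither the retest interval nor the rate of transient negatives is documented, so the net sign is not established.
- *The bias is unequal between persistent and non-persistent patients.* This is plausible: persistent status needs a PCR at day 21 or later, non-persistent status needs no late test, and Section 4.4 mixes inpatients and outpatients. No section gives test frequency by group, so neither size nor direction can be derived.
- *The main contrast will show a false hazard ratio.* Under the Weibull model with median 14 days, weekly against fortnightly testing gives a clearance hazard ratio of about 0.77 when true clearance is identical. The persistent and non-persistent groups cannot have identical clearance, because they are defined by late positivity. Such a figure could apply at most to centres or covariates with unequal testing.
- *Prevalence is inflated.* In the same model (f = 0), the share whose first negative falls at day 21 or later rises from a true 28% to 64% with tests every 21 days. That share is not the primary endpoint, which needs an observed positive at day 21 or later plus symptoms or signs. The share with such an observed positive falls with sparser testing, from about 24% at 3-day to about 12% at 21-day intervals.

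**Conclusion.** The concern holds as a defect of definition and analysis. The end of shedding is interval-censored, the plan treats it as exact, and the rule can contradict the protocol's own definition of persistence.

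With an accurate test and regular testing from a random start, the excess is half the retest interval. That is material against a 21-day threshold once retesting is fortnightly or sparser (7 days or more). The intervals, clearance distributions and negative rates are illustrative assumptions. What rests on the documents alone is the absence of a schedule, the exact-date analysis, and the day-12/day-25 contradiction.

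Net direction is unknown, and a difference in error between groups is possible but not shown.

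A separate problem remains whatever method is used. Comparing shedding between groups defined by PCR positivity at day 21 or later is largely circular, and interval censoring does not cure that.

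**What to change.** **Section 3.3.** Record the last positive PCR date and the first negative PCR date with no later positive in the same episode. Define an episode so that one positive cannot count both as continued shedding and as re-infection. If the day-25 positive in Step 4 belongs to the same episode, shedding then runs past day 25 and agrees with persistent status.

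**Section 4.8.**
- Analyse shedding as interval-censored between the two dates: Turnbull estimate, and an interval-censored Weibull or proportional-hazards model.
- Right-censor patients never shown negative at their last positive, and state how deaths before clearance are handled.
- For the description in persistent patients, give the Turnbull median in place of a mean or median of recorded values.
- Report the number of PCRs and the retest interval by group. State that these methods assume test timing is non-informative, which may fail where testing follows clinical status.
- Reconcile the statements on whether shedding is compared between groups or described in persistent patients only. If a comparison stays, acknowledge its circularity.

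**Cost.** One extra date field from the same records, an episode definition, SAP wording and standard software. No additional testing and no change to care. Confidence intervals will be wider, which reflects what the samples actually determine.

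### Imaging alterations count only if seen on a routine-care chest CT, yet the rate divides by all patients, so the prevalence reported for persisters is a lower bound rather than an estimate

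*Combined protocol and SAP*

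**What the plan says.** Four statements in the combined protocol and SAP bear on this.

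- **Endpoint (3.3).** Imaging alteration is "the presence of new ground-glass and/or crazy paving and/or interstitial infiltrates at chest CT scan during the persisting infection", with the window given as "starting from 21 days after the first positive test until viral clearance". CT is the only modality that counts.
- **Persistence (3.3).** A patient is a persister with a positive PCR at 21 days or later plus symptoms or signs drawn from a wider list: "fever, dyspnea, hypoxemia, changes on chest-X ray or CT scan". Chest X-ray changes suffice here.
- **Conduct (4.3, 4.7).** In 4.3, "screening for persisting SARS-CoV-2 infection and therapeutic management of all patients will be carried out by the attending physicians according to routine practice". In 4.7, "Data sources will be clinical charts and hospital electronic records". No section schedules a chest CT.
- **Analysis (4.8).** "Re-infection and imaging alterations rates will be calculated as the ratio of the number of events to the overall number of patients", and then "the comparison between persisters and non-persisters will be carried out by calculating the corresponding risk ratios". A multiple logistic model for imaging alteration follows. The section closes by saying that the secondary endpoints will be described for persisters only.

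There is no scanned-only denominator, no category for patients without a CT and no missing-data rule for imaging. Section 4.4.3 calls 1,000 patients adequate for the imaging analysis but gives no expected rate and no scan coverage.

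**The concern.** The numerator can be filled only by patients whose physician ordered a CT in the window. The denominator holds everyone. In this ratio, not scanned and scanned with no alteration are the same thing.

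The two definitions in 3.3 make this visible in single patients. Someone classed as a persister because of X-ray changes, with no CT after day 21, enters the imaging rate as a non-event although the chart documents a chest abnormality.

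Radiological outcome is part of the secondary objective in 3.2. A reader would take the published figure as the frequency of lung alterations in persisting infection. In an international multicentre study it would also differ between centres that scan readily and centres that do not, with no difference in lung disease.

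**Working it through.** The plan states no numerical figure for imaging, so there is none to reproduce; the table in 4.4.3 concerns 120-day mortality only.

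**Inputs**
- From the documents: CT-only event and window (3.3); all-patient denominator (4.8); about 300 prolonged infections expected (4.4.3). The 300 rests on viral shedding, not on the full persistence definition, and is used only to turn percentages into counts.
- Not in the documents, so assumed over a range: *s*, the share of persisters with a CT in the window (40% to 80%), and *q*, the share of those scanned who show an alteration (30% to 70%).

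**Step 1. What the data can show among persisters**
- Rate as planned: *s* × *q*. This is the true rate only if no unscanned patient has an alteration, so it is a lower bound.
- Rate among scanned: *q*.
- Upper bound, if every unscanned patient had an alteration: *s* × *q* + (1 − *s*).
- Width between the bounds: 1 − *s*, whatever *q* is.

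| Scanned (*s*) | Positive among scanned (*q*) | Planned rate (lower bound) | Upper bound |
|---|---|---|---|
| 40% | 30% | 12% | 72% |
| 40% | 50% | 20% | 80% |
| 40% | 70% | 28% | 88% |
| 60% | 30% | 18% | 58% |
| 60% | 50% | 30% | 70% |
| 60% | 70% | 42% | 82% |
| 80% | 30% | 24% | 44% |
| 80% | 50% | 40% | 60% |
| 80% | 70% | 56% | 76% |

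In counts, for 300 persisters with *s* = 60% and *q* = 50%: 180 scanned, 90 altered, 120 not scanned. The planned rate is 90/300 = 30%, the scanned-only rate is 90/180 = 50%, and the upper bound is (90 + 120)/300 = 70%.

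**Step 2. Dependence on CT practice**
Take two centres with *q* = 50%, one scanning 40% of its persisters and the other 80%. Their planned rates are 20% and 40%, although the finding among scanned patients is the same.

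**Step 3. Why the shortfall cannot be sized**
Assume a true rate of 40% and 70% scanned.
- Scanning unrelated to disease: planned rate 0.70 × 0.40 = 28%; scanned-only 40%.
- Every altered lung among those scanned: planned rate 40%; scanned-only 40/70 = 57%.

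With the same coverage and the same truth, the planned rate is 12 percentage points too low in the first case and correct in the second. The scanned-only rate is correct in the first and 17 points too high in the second. The truth depends on how physicians choose whom to scan, which the documents do not describe. Neither rate can stand alone.

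**Step 4. Non-persisters**
Applying the definitions in 3.3 in turn:
- Cleared before day 21: the window never opens, so no event is possible.
- PCR-positive at or after day 21 with CT changes: the persistence definition is met, so the patient is a persister.
- No repeat PCR: clearance is undated, and this is the main route by which an event could fall among non-persisters.

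Non-persisters can therefore have almost no imaging events, however often they are scanned.

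**The case against.** **Inferred, not stated.** Section 4.3 names screening and therapeutic management, not imaging. The eCRF is not shown and may already record whether a CT was done. Both points are fair. But with no CT schedule anywhere and charts as the only source, CT by clinical choice is the natural reading, and an eCRF field would not change the ratio that 4.8 prescribes.

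**X-ray and CT may properly differ.** A case definition can accept broader evidence than a specific CT outcome, so the two parts of 3.3 do not contradict each other. That stands. The difficulty is only that the denominator turns an absence of CT into an absence of alteration.

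**Unequal scanning and the risk ratio.** A reader might infer that more frequent scanning of persisters manufactures the group difference. With a 40% true rate in both groups and 70% against 30% scanned, the rates would be 28% and 12%, a ratio of 2.3. The documents do not support this: under 3.3, non-persisters have almost no opportunity for an event (Step 4), so a 12% rate there does not describe this plan. The comparison is uninterpretable for that separate reason, and a scanned-only denominator does not repair it.

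**Switching to a scanned-only rate.** A reader might also infer that dividing by scanned patients gives the right prevalence. If physicians scan the patients they suspect, it overstates it (57% against 40% in Step 3). This objection stands in full, so the scanned-only rate should be shown beside the bounds and should not replace them.

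**Conclusion.** The point holds for the prevalence of imaging alterations among persisters. Under 3.3 and 4.8 as written, the reported figure is a floor that depends on CT practice, presented as a prevalence. That the figure is a floor needs no assumption about scan rates, only that CT findings are read correctly: if any persister with alterations has no CT in the window, the figure is too low.

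The size of the shortfall cannot be derived from the documents. The unresolved range equals the unscanned share, for example 40 percentage points if 60% are scanned, but that coverage is an assumption. The documents do not support a fixed multiplier, because scanning may be related to disease, and they do not support a stated inflation of the risk ratio. The endpoint is secondary and the remedy is cheap, so the wording should be corrected before the data are analysed.

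**What to change.** In 4.8:
1. Classify each persister as altered on CT, not altered on CT, or not assessed (no CT in the window). Record chest X-ray findings separately.
2. Report the number and percentage scanned, by group and by centre.
3. Present three figures together: the all-patient rate, labelled a lower bound; the rate among scanned patients, labelled conditional on clinical indication; and the upper bound if all unscanned patients were altered.
4. State that unscanned patients are not entered as unaltered in the logistic model.

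These changes do not rescue the comparison of persisters with non-persisters, which needs its own resolution because of the window and the overlapping definitions. The closing sentence of 4.8, which limits the secondary endpoints to persisters, should be reconciled with that comparison at the same time.

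The cost is SAP wording and one extra field (CT in window yes/no, with date) from charts already being read. No additional scans are needed. The downside is a wider and less favourable range in place of a single figure.

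### The re-infection comparison between persisters and non-persisters may partly reflect who was tested more, and the plan has nothing to show or limit this.

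*Combined protocol and SAP*

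**What the plan says.** Section 3.3 lists re-infection within 120 days as a secondary endpoint and defines it as a "new positive test with or without symptoms after viral clearance has been achieved". The same section defines a persister by symptoms or signs together with a "positive SARS-CoV-2 PCR ≥ 21 days after the time 0".

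On testing, section 4.3 says that "screening for persisting SARS-CoV-2 infection and therapeutic management of all patients will be carried out by the attending physicians according to routine practice". Section 4.7 adds: "Data sources will be clinical charts and hospital electronic records". No section sets a testing schedule after clearance.

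On analysis, section 4.8 says that re-infection rates "will be calculated as the ratio of the number of events to the overall number of patients", and that "the comparison between persisters and non-persisters will be carried out by calculating the corresponding risk ratios". It continues: "A multiple logistic regression model will assess the relationship between exposure and re-infection (image alteration) net of the potential confounders". The listed covariates include duration of hospital stay, intensive care admission, chemotherapy, superinfections and catheter days. They do not include the number, frequency or reason of SARS-CoV-2 tests. No analysis restricted to symptomatic re-infection is planned.

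**The concern.** A re-infection with symptoms has some chance of prompting a test. One without symptoms is found only if a test is done for another reason. When both count equally and testing is not scheduled, the observed risk in each group is the true risk multiplied by that group's chance of detection. If those chances differ, the risk ratio carries the difference.

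There is a reason in the plan itself to think that they may differ. A patient who is not re-tested at or after day 21 can only be a non-persister, so the persister group is selected partly on having been re-tested. The study is also multicentre and joins a retrospective period from January 2022 to a prospective year, so testing habits may vary, and the covariate list includes neither centre nor recruitment period.

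At stake is how one secondary comparison is read. A ratio away from 1 could be reported as an effect of persistence on re-infection when part or all of it is surveillance, or a real difference could be masked. This point does not bear on the primary prevalence estimate.

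**Working it through.** **The plan's own figures.** The only power figures (section 4.4.3) concern 120-day mortality. They reproduce with the Freedman formula at allocation 0.43: for survival 0.97 v 0.93, 931.3 against the stated 933; for 0.95 v 0.90, 895.9 against 897. None addresses re-infection. The documents give no re-infection rate, test frequency or asymptomatic share, so what follows is illustration on assumed inputs.

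**Effect on the ratio.** Assume equal true risk in both groups (true ratio 1.0), detection of 90% of symptomatic re-infections in both, and an asymptomatic share s of 0.3 or 0.5. Let q1 and q0 be the detection of asymptomatic re-infection in persisters and non-persisters. Then

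observed ratio = [(1 − s) × 0.9 + s × q1] / [(1 − s) × 0.9 + s × q0]

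| q1 v q0 | s = 0.3 | s = 0.5 |
|---|---|---|
| 60% v 20% | 0.81/0.69 = 1.17 | 0.75/0.55 = 1.36 |
| 80% v 10% | 0.87/0.66 = 1.32 | 0.85/0.50 = 1.70 |
| 40% v 30% | 0.75/0.72 = 1.04 | 0.65/0.60 = 1.08 |
| 20% v 60% | 0.69/0.81 = 0.85 | 0.55/0.75 = 0.73 |

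With equal detection the ratio is 1.0. The range over these cases is 0.73 to 1.70 and includes near-null values.

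**Effect on a significance test.** Take the 300 and 700 patients expected in section 4.4.3, two-sided alpha 0.05, no true difference, and overall detection d1 v d2. Then p1 = r × d1 and p2 = r × d2 for true risk r, and

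P(p < 0.05) = Φ[(|p1 − p2| − 1.96 × SE0) / SE1],

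with SE0 the pooled and SE1 the unpooled standard error. For r = 10% and detection 75% v 50%: p1 = 0.075, p2 = 0.05, pooled risk 57.5/1000 = 0.0575, SE0 = 0.01606, SE1 = 0.01730, and Φ(−0.375) = 35%.

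| Detection | Ratio | r = 5% | r = 10% |
|---|---|---|---|
| 60% v 50% | 1.20 | 7% | 10% |
| 75% v 50% | 1.50 | 21% | 35% |
| 80% v 40% | 2.00 | 45% | 72% |

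With equal detection it is 5%.

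**A bias the other way.** Follow-up is 120 days from diagnosis (section 4.5), and the denominator is all patients, so those who clear later have fewer days at risk. At a constant low hazard and equal testing, the ratio is about the ratio of days left. For assumed clearance at day 30 v 10 that is 90/110 = 0.82, and at day 60 v 14 it is 60/106 = 0.57. The net direction is therefore unknown.

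**The case against.** No section says that the groups are tested differently after clearance. The day-21 rule shows that classification depends on re-testing, but not what happens afterwards. Testing before haematological treatment could apply equally to both groups, which would leave no bias. A reader might infer that persisters are in fact tested more, so that any excess is only surveillance. The documents do not support that, and the illustration runs on both sides of 1.

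A reader might also take section 4.3 to hand re-infection testing to the physicians. Its sentence concerns screening for persisting infection and therapeutic management. For re-infection, the premise rests on the absence of any schedule and on the chart-based data source. That is enough for the concern, but it is a different basis.

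Nor can one say that the logistic model is unable to remove any of the bias. Hospital stay, intensive care admission and similar covariates may track contact with care. They are at best partial proxies, they may miss swabs taken in outpatients (who are eligible under section 4.4), and they do nothing for the crude risk ratio.

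The most substantial objection is to replacing the endpoint by symptomatic cases. Persisters are defined partly by persisting or recurring symptoms or signs, and section 3.3 does not require symptoms to resolve before clearance. Lingering symptoms plus an incidental positive could be misread as symptomatic re-infection, mainly in persisters. Counting all positives is also defensible for a virological outcome. This stands, and it is why the symptomatic analysis belongs beside the planned one and needs a new-onset condition.

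Finally, the last paragraph of section 4.8 says that secondary endpoints are described only in persisters. That conflicts with the risk-ratio text in the same section and with the comparative objective in section 3.2. The passages must be reconciled, but the re-infection comparison is explicitly specified.

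**Conclusion.** The concern holds in conditional form. Any new positive counts, testing after clearance is unscheduled, exposure status depends on re-testing, and neither the crude ratio nor the model contains a measure of testing. The comparison may therefore partly reflect testing intensity. The range of 0.73 to 1.70 at a true ratio of 1.0 rests wholly on assumed detection rates and asymptomatic shares. It shows what is possible and is not an estimate of the bias. Shorter time at risk in persisters and the lack of a definition of viral clearance affect the same ratio and are not cured by the change proposed here. Since the endpoint is secondary and the remedy is cheap, this is a worthwhile improvement and not a flaw that undermines the study.

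**What to change.** In section 4.8:

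- Keep the risk ratio and logistic model for any new positive test.
- Add a pre-specified comparison, again by risk ratio and logistic model, restricted to test-confirmed re-infection with new-onset symptoms, meaning symptoms not continuous with the index episode.
- Tabulate SARS-CoV-2 tests per person-month after clearance, by group. The table needs a stated start date. Section 3.3 does not define viral clearance; the first negative PCR, which it uses to end viral shedding, is the nearest existing wording.
- State that an excess seen only in asymptomatic positives, or alongside unequal testing, will not be interpreted as higher re-infection risk.

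No protocol-driven testing is needed. The cost is extraction of test dates and a symptom flag from charts already being read. The symptomatic analysis will have fewer events and a wider interval, and some misclassification from lingering symptoms may remain. Symptom-triggered testing could still differ between groups; the table of test rates would help readers judge this.
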